**CONFIDENTIAL**

209699 (RSV OA=ADJ-003)  
Protocol Final Version 1

re-screening visit occurs. Only data from the re-screening visit, if it occurs, will be taken into consideration and recorded in the eCRF. The subject can only be randomized once the investigator receives the results and confirms the eligibility criteria.

 Any vaccination administered up to 5 years before administration of the first dose of study vaccine should be recorded in the eCRF.

 If deemed necessary by the investigator.

 Blood sampling to be performed before vaccination.

 Only re-instruction on the use of eDiary device at Visit 4.

 Intercurrent medical conditions will only be collected up to Visit 6 (Day 91); thus, not during Assessment visits for potential RSV-RTI occurring after Visit 6.

Whenever possible, the investigator should arrange study visits within the intervals described in [Table 2](#).

**Table 2** Intervals between study visits

Interval	Length of interval	Allowed interval
Screening Visit → Visit 1		3 – 30 days*
Visit 1→Visit 2	7 days	7 - 10 days
Visit 1→Visit 3	30 days	30 - 37 days
Visit 1→Visit 4	60 days	55 - 65 days
Visit 4→Visit 5	7 days	7 - 10 days
Visit 4→Visit 6	30 days	30 - 37 days
Visit 4→Phone call 1	180 days	180 - 200 days
Visit 4→Phone call 2	365 days	365 - 395 days

\* Visit 1 should take place no longer than 30 days after the Screening Visit. In case Visit 1 occurs more than 30 days after the Screening Visit, a re-screening visit should be scheduled before Visit 1 during which blood sample collection for safety laboratory assessment must be repeated (maximum one re-screening per subject is allowed). Only laboratory results from the re-screening visit, if it occurs, will be taken into consideration and recorded in the eCRF. Medical history, physical examination and review of inclusion/exclusion criteria must be repeated if a re-screening visit occurs. The subject can only be randomized once the investigator receives the results and confirms the eligibility criteria.

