### 8.4.2.1. Blood sampling for safety or immunogenicity response assessments

Blood samples will be taken during certain study visits as specified in Section 2. Refer to the SPM for more details. Blood sampling at vaccination visits needs to be performed before vaccination.

- A total volume of approximately 5.5 mL of blood should be drawn from all subjects for hematology and biochemistry analysis at each pre-defined time point. After centrifugation, serum samples should be kept at room temperature (20 to 25°C) until shipment.
- A volume of approximately 10 mL of whole blood (to provide ~3.3 mL of serum) should be drawn from all subjects for analysis of the humoral immune response at each pre-defined time point. After centrifugation, serum samples should be kept at -20°C or below until shipment.
- The overall volume of blood that will be collected from each subject during the entire duration of the study is approximately 67.5 mL.

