**Table 11 Immunological read-outs**

Blood sampling time point*	Sub-cohort	No. subjects	Component	Components priority rank
Type of contact and time point				
Humoral immunity (on serum samples)				
Visit 1 (Day 1)	Pre-Day 1	All subjects	~ 40	RSV-A neutralizing antibody Anti-RSVPreF3-specific IgG antibody RSV-B neutralizing antibody
Visit 3 (Day 31)	PI D31	All subjects	~ 40	RSV-A neutralizing antibody Anti-RSVPreF3-specific IgG antibody
Visit 4 (Day 61)	PI D61	All subjects	~ 40	RSV-A neutralizing antibody Anti-RSVPreF3-specific IgG antibody
Visit 6 (Day 91)	PII D91	All subjects	~ 40	RSV-A neutralizing antibody Anti-RSVPreF3-specific IgG antibody RSV-B neutralizing antibody

Pre-Vacc: Pre-vaccination; PI DX= Post-Dose 1 Study Day X; PII DX: Post-Dose 2 Study Day X

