## 9.2. Discontinuation of study vaccine

A ‘withdrawal’ from the study vaccine(s) refers to any subject who does not receive the complete treatment, i.e. when no further planned dose is administered from the date of withdrawal. A subject withdrawn from the study vaccine(s) may continue further study procedures (safety or immunogenicity) if planned in the study protocol, as deemed appropriate by the investigator.

Primary reason relative to premature discontinuation of the study vaccine(s) will be documented on the Vaccine Administration screen of the eCRF. The investigator will document whether the decision to discontinue further vaccination was made by the subject himself/herself or by the investigator, as well as which of the following possible reasons was responsible for withdrawal:

- Adverse event requiring expedited reporting
- Non-serious adverse event (specify)
- Unsolicited non-serious adverse event
- Solicited adverse event
- Not willing to be vaccinated
- Other (specify).

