#### 4.2.2. Elimination from Per-protocol analysis Set (PPS)

##### 4.2.2.1. Excluded subjects

A subject will be excluded from the PPS analysis under the following conditions

- For codes 800, 900, 1030, 1050 and 1060: subjects will be eliminated for all visits.
- For codes 1040, 1070, 1080, 1090, 2010, 2040, 2060, 2080: subjects will be eliminated from a specific visit (at which the condition is met) onwards.
- For codes 2090, 2100, 2120: subjects will be eliminated for the specific visit at which the condition is met.

Code	Condition under which the code is used	Visit (timepoints) where the code is applicable	Applicable for analysis set
800	Fraudulent data	All	ES and PPS for analysis of immunogenicity
900	Invalid informed consent or other GCP non-compliance	All	ES and PPS for analysis of immunogenicity
1030	Study vaccine not administered at all	All	ES and PPS for analysis of immunogenicity
1040	Administration of concomitant vaccine(s) forbidden in the protocol Any investigational or non-registered vaccine other than the study vaccine used during the study period	All	PPS for analysis of immunogenicity

Code	Condition under which the code is used	Visit (timepoints) where the code is applicable	Applicable for analysis set
	A vaccine not foreseen by the study protocol administered during the period starting 30 days before the first dose and ending 30 days after the last vaccine dose, except for inactivated and subunit influenza vaccines which can be administered up to 14 days before or from 30 days after each vaccination.		
1050	Randomization failure	All	PPS for analysis of immunogenicity
1060	Randomization code was broken	All	PPS for analysis of immunogenicity
1070	Vaccination not according to protocol Incomplete vaccination course Subject was vaccinated with the correct vaccine but containing a lower volume Wrong replacement or study vaccine administered (not compatible with the vaccine regimen associated to the treatment number) Route of the study vaccine is not intramuscular Wrong reconstitution of administered vaccine	Vaccination visits 1 and 4	PPS for analysis of immunogenicity
1080	Vaccine temperature deviation Vaccine administered despite a Good Manufacturing Practices (GMP) no-go temperature deviation	Vaccination visits 1 and 4	PPS for analysis of immunogenicity
1090	Expired vaccine administered	Vaccination visits 1 and 4	PPS for analysis of immunogenicity

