2010	Protocol violation (inclusion/exclusion criteria)	All	PPS for analysis of immunogenicity
2040	Administration of any medication forbidden by the protocol Any investigational or non-registered medication used during the study period Immunosuppressants or other immune-modifying drugs administered chronically (i.e., more than 14 consecutive days in total) during the study period Long-acting immune-modifying drugs administered at any time during the study period Immunoglobulins and/or any blood products administered during the study period	All	PPS for analysis of immunogenicity
2060	Intercurrent medical condition Subjects may be eliminated from the PPS if, during the study, they incur a condition that has the capability of altering their immune response or are confirmed to have an alteration of their initial immune status (other than RSV infection).	All	PPS for analysis of immunogenicity
2080	Subjects did not comply with vaccination schedule number of days between dose 1 and dose 2 is outside [55-65 days]	Visit 4	PPS for analysis of immunogenicity

Code	Condition under which the code is used	Visit (timepoints) where the code is applicable	Applicable for analysis set
2090	Subjects did not comply with blood sample schedule Number of days between dose 1 and visit 3 blood sample is outside [30-37 days] Number of days between dose 2 and visit 6 blood sample is outside [30-37 days]	Visits 3 and 6	PPS for analysis of immunogenicity
2100	Serological results not available post-vaccination No immunological result at visit x for all 2 following tests: RSV A Neutralising antibody titer and RSVPreF3-specific IgG antibody concentration	Visits 3, 4, 6	PPS for analysis of immunogenicity
2120	Obvious incoherence or abnormality or error in data Unreliable released data as a result of confirmed sample mismatch or confirmed inappropriate sample handling at lab	Visits 1, 3, 4, 6	PPS for analysis of immunogenicity

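### A missed or faulty Dose 2 removes a valid Day 61 antibody result, drawn before that dose, from the per-protocol immunogenicity analysis

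*SAP*

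**What the plan says.** SAP 4.2.2.1 sorts the per-protocol elimination codes into three kinds: all visits, one visit only, and from a visit forward. Codes 1070 (vaccination not per protocol, including an incomplete course), 1080 (temperature deviation) and 1090 (expired vaccine) are of the third kind: "subjects will be eliminated from a specific visit (at which the condition is met) onwards". The code table applies them at vaccination Visits 1 and 4.

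Visit 4 is also a serology visit. Protocol 8.4.2.1 states: "Blood sampling at vaccination visits needs to be performed before vaccination". Footnote 4 to the schedule of activities (Protocol Section 2, Table 1) repeats this for Visits 1 and 4. Protocol Table 11 labels the Visit 4 sample PI D61, with the key "PI DX= Post-Dose 1 Study Day X". SAP code 2100, for missing post-vaccination serology, covers Visits 3, 4 and 6, so the SAP itself treats Visit 4 as a post-vaccination result.

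Code 2080, also a from-this-visit-forward code, applies at Visit 4 when the "number of days between dose 1 and dose 2 is outside [55-65 days"]. Code 2090 sets sample windows for Visits 3 and 6 only.

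SAP 5.3 makes the per-protocol set primary for immunogenicity. It adds an Exposed Set analysis if, in any group at any timepoint, 10% or more of vaccinated subjects with serological results are excluded.

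**The concern.** The sample and the dose share a visit number but happen in a fixed order: blood first, vaccine second. A rule that works on visit numbers cannot see that order. When Dose 2 is under-filled, wrongly reconstituted, expired, temperature-compromised or not given, the rule removes a result that reflects Dose 1 alone.

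Day 61 RSV-A neutralizing titre and RSVPreF3 IgG are named secondary endpoints. As written, their primary GMT/GMC depends on correct receipt of a dose given after the blood was drawn. The main cost is avoidable loss of valid data in groups of about 20. A lesser worry is selective loss: Protocol 7.7 withholds Dose 2 after certain post-Dose 1 events, so the removed subjects need not be a random subset. Some of them may carry code 2040 or 2060 anyway, and nothing in the documents links the other reasons to antibody level.

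The problem arises only if the Visit 4 sample was drawn. For subjects who do not receive Dose 2, Protocol 9.2 allows this: "A subject withdrawn from the study vaccine(s) may continue further study procedures (safety or immunogenicity) if planned in the study protocol", as the investigator judges appropriate.

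**Working it through.** **Rule applied to the serology visits.** Humoral samples are taken at Visits 1, 3, 4 and 6. For a fault met at Visit 4:

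- as written: Visits 1 and 3 kept; 4 and 6 removed;
- if elimination starts with the first sample after the affected dose: Visits 1, 3 and 4 kept; 6 removed.

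The difference is one Day 61 result per affected subject for each of the two assays. A Dose 1 fault is not at issue: it properly removes the later visits.

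**Code 2080.** It tests the dose interval, not the sample time. A sample drawn 55-65 days after Dose 1, with Dose 2 given on a later date beyond day 65, is removed although the sample was on time.

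The plan states no figure for this rule, so the following only sizes the effect. Group size is 20 (Protocol 10.1.1).

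**Precision.** The 95% CI half-width on the log scale, in SD units, is t(0.975, n-1)/√n.

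| n | Half-width | Ratio to n = 20 |
|---|---|---|
| 20 | 2.0930/√20 = 0.468 | 1 |
| 19 | 0.482 | 1.030 |
| 18 | 0.497 | 1.063 |

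**Exposed Set trigger.** 1/20 = 5%, not met; 2/20 = 10%, met. With 18 subjects with results: 1/18 = 5.6%, not met; 2/18 = 11.1%, met.

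**Selective loss.** Removing a value x shifts the mean log titre by |x - mean|/(n-1). The largest possible |x - mean| in a sample is s(n-1)/√n, so the largest shift is s/√n = 0.224 SD at n = 20. That is 0.224/0.468 = 0.48 of the CI half-width. A subject 2 SD from the mean shifts it by 2/19 = 0.105 SD.

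**How often a loss would go unaccompanied by the Exposed Set analysis.** The documents give no Dose 2 fault rate. Let p be an assumed chance per subject of a Dose 2 fault with the Visit 4 sample drawn, independent across subjects, with p0 = (1-p)^20 and p1 = 20p(1-p)^19.

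- A: at least one loss, neither group reaching two = (p0+p1)² - p0².
- B: exactly one loss in the RSV group, placebo at most one = p1(p0+p1).

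| p | A | B |
|---|---|---|
| 1% | 0.298 | 0.162 |
| 2% | 0.438 | 0.256 |
| 5% | 0.413 | 0.278 |
| 10% | 0.139 | 0.106 |

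Over all p, A peaks at 0.479 (p = 3.1%) and B at 0.301 (p = 3.6%). Both are upper bounds, because exclusions for other reasons also count towards the trigger.

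**The case against.** The strongest reply is that this hardly matters. No hypothesis, power calculation or decision rule rests on Day 61, the primary objective is safety on the Exposed Set, and the removed value remains in the Exposed Set. That stands as a statement of size. It does not justify discarding a valid result.

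The bounds above are also loose. The trigger counts exclusions under any code, in either group and at any timepoint. Protocol 5.3 plans for 10% non-evaluable subjects, which is 2 in 20. Suppose other exclusions occur independently at rate q, all with serology and at the same timepoint. Given one Dose 2 loss, the chance that the Exposed Set analysis is not run is (1-q)^19 × P(at most one in the other group): 64% at q = 2%, 28% at 5% and 5% at 10%. Non-evaluable subjects without serology do not count, so 10% is the upper end. The point is fair, and the figures in A and B should be read as ceilings. Fault rates of 5-10% may also be high, given the controls on treatment allocation, temperature excursions and replacement doses.

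Code 2080 is a weak case: the protocol reschedules the whole visit, so blood and dose normally move together. It should be rare, but the gap is real when they separate.

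Finally, the SAP does not say at which visit an incomplete course is met. Since only Visits 1 and 4 are listed, Visit 4 is the natural reading for a missed Dose 2, though this is an inference. The other Dose 2 faults do not depend on it.

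**Conclusion.** The concern holds. Taken literally, the SAP removes from its primary immunogenicity set a Day 61 result that the deviation could not have affected, and no text exempts it. Programmers may already keep such samples, but the SAP does not tell them to.

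The consequence is small: about 3% on CI width for one loss in 20 and about 6% for two, with a shift of at most one standard error from any single removal. How often it would occur is unknown; the frequencies rest on assumed, independent fault rates and are upper bounds. It is worth correcting because the logic is clear and the remedy nearly free, not because the trial's conclusions are at risk.

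**What to change.** Add to SAP 4.2.2.1:

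> When code 1070, 1080 or 1090 arises from Dose 2 at Visit 4, elimination starts at Visit 6 and the Visit 4 pre-dose sample is retained. When code 2080 is met, the Visit 4 sample is retained if it was drawn 55-65 days after Dose 1; otherwise elimination starts at Visit 4.

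The first sentence should be stated to cover a Dose 2 that was not given, which also settles the visit at which an incomplete course is met. The 55-65 day range is the SAP's own.

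Make the change before database freeze and before the Day 91 analysis, when SAP 7.1 has the statistician unblinded. It needs no new data and no change to visits, sampling or tables.

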## 4. ANALYSIS SETS

### 4.1. Definition

For purposes of analysis, the following analysis sets are defined:

Analysis Set	Description
Enrolled	All subjects who sign informed consent.
Exposed	All subjects who received at least 1 dose of the study treatment. The allocation in a group is done in function of the administered treatment.
Per Protocol	All subjects who received at least 1 dose of the study treatment to which they are randomized and have post-vaccination data minus subjects with protocol deviations that lead to exclusion.

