#### 4.2.1. Elimination from Exposed Set (ES)

Code 1030 (Study vaccine not administered at all), 800 (Fraudulent data) and code 900 (invalid informed consent or other GCP noncompliance) will be used for identifying subjects eliminated from ES.

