## **5.3. Immunogenicity**

The primary analysis will be based on the Per Protocol set for analysis of immunogenicity. If in any study group and at any timepoint, the percentage of vaccinated subjects with serological results excluded from the Per Protocol set for analysis of immunogenicity is 10% or more, a second analysis based on the Exposed set will be performed to complement the Per Protocol analysis.

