##### 10.1.2.2. Laboratory data

Missing laboratory results (including immunological data) will not be replaced.

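### If the complementary Exposed Set immunogenicity analysis is triggered, as written it includes antibody results already coded 2120 as unreliable (minor)

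*SAP*

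**What the plan says.** SAP 4.1 defines the ES as "All subjects who received at least 1 dose of the study treatment", with no condition on the validity of individual results. SAP 4.2.1 names three codes that "will be used for identifying subjects eliminated from ES": 800 (fraud), 900 (invalid consent or other GCP failure) and 1030 (never vaccinated). The code table in SAP 4.2.2.1 agrees, because only these three are marked for both the ES and the PPS.

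Code 2120 is marked for the PPS only, at Visits 1, 3, 4 and 6. Its condition is "Unreliable released data as a result of confirmed sample mismatch or confirmed inappropriate sample handling at lab". Its reach within the PPS is one visit: "For codes 2090, 2100, 2120: subjects will be eliminated for the specific visit at which the condition is met".

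Under SAP 5.3 (and Protocol 10.3.3) the primary immunogenicity analysis uses the PPS. If, in any group at any timepoint, "the percentage of vaccinated subjects with serological results excluded from the Per Protocol set for analysis of immunogenicity is 10% or more", then "a second analysis based on the Exposed set will be performed to complement the Per Protocol analysis".

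**The concern.** Most PPS-only codes describe a departure from the protocol or a change in the subject: a forbidden vaccine or drug, a dosing or schedule error, an eligibility failure, an intercurrent condition. The antibody result is still a genuine measurement of that subject, and restoring it is the purpose of an ES analysis. Code 2100 has no result to restore.

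Code 2120 is different. A mismatched sample yields a value that is not that subject's, and a mishandled one yields a value the SAP itself calls unreliable. Neither becomes usable because the population definition is wider.

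The ES run should show whether the PPS exclusions changed the immunogenicity picture. If confirmed laboratory errors come back with the excluded subjects, a difference between ES and PPS could reflect those errors instead.

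**Working it through.** **1. Does any other rule withdraw a 2120 result from the ES?**

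| SAP section | What it covers | Removes a 2120 result from the ES? |
|---|---|---|
| 4.2.1 | Codes 800, 900, 1030 | No |
| 4.2.2.1 | 2120, PPS only, affected visit | No |
| 10.1.2.2 | "Missing laboratory results (including immunological data) will not be replaced" | No; the result is present, not missing |
| 10.1.3.2 | Derives values by format, cut-off and ULOQ | No; validity is not checked |
| 5.4.2.4 | First-result and retest rules | No; safety laboratory data only |

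**2. When does the ES run happen?** The plan's own threshold is 10%. With 20 in a group, 1/20 = 5% is not enough and 2/20 = 10% is. With 16 in a group, 1/16 = 6.25% and 2/16 = 12.5%, so two subjects are needed throughout the range 16 to 20. A 2120 subject has a released result and so counts towards the trigger. Two such cases in one group at one visit would start the analysis that then contains them.

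For context, Protocol 5.3 plans for 10% non-evaluable: 40 × (1 − 0.10) = 36, or 2 per group if evenly spread. The two 10% figures are not the same quantity, because non-evaluable subjects without serological results do not count towards the trigger.

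**3. Size on planned outputs.** The documents give no titre spread or expected effect, so these inputs are assumptions: n = 20 per group, log10 SD s = 0.35, true RSV/placebo GMT ratio R of 5 to 20, and one post-vaccination sample swapped between an RSV and a placebo subject. This swap is 1/20 = 5% per group, so the scenario also assumes that the ES run was triggered by at least one further exclusion.

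- RSV GMT is multiplied by R^(−1/n), and placebo GMT by R^(1/n).
- Expected SD after the swap is √(s² + (log10 R)²/n). The ratio of this to s gives the widening of the log-scale confidence interval.

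| R | RSV GMT | Placebo GMT | SD after swap | CI width |
|---|---|---|---|---|
| 5 | ×0.923 (−8%) | ×1.084 (+8%) | √(0.1225 + 0.0244) = 0.383 | ×1.10 |
| 10 | ×0.891 (−11%) | ×1.122 (+12%) | √(0.1225 + 0.0500) = 0.415 | ×1.19 |
| 20 | ×0.861 (−14%) | ×1.162 (+16%) | √(0.1225 + 0.0846) = 0.455 | ×1.30 |

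The GMT shift does not depend on s; the widening does. At R = 10 it is ×1.25 for s = 0.3 and ×1.10 for s = 0.5.

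A swap within one group averages the same 20 values, so the GMT at that visit does not move.

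**4. A wrong Visit 1 value.** SAP 5.3.1.1 divides each post-vaccination result by the Day 1 result. In the ES, one baseline too high by an assumed factor F multiplies the group's geometric mean fold increase by F^(−1/20) at each of Days 31, 61 and 91. That is ×0.97 for F = 2 and ×0.86 for F = 20. A baseline too low by F gives the inverse.

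**The case against.** The strongest reply is that little depends on this. The primary analysis is the PPS, where 2120 does apply. The ES analysis is conditional and only complements it. Immunogenicity is secondary or tertiary and, under SAP 6, descriptive. No test, sample size or safety endpoint is touched. Harm requires both a confirmed laboratory error still in the dataset and the 10% trigger. All of this stands, and it sets the severity.

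It can also be said that the laboratory would withdraw such results in practice. That is possible, but neither document says so, and code 2120 refers explicitly to released data.

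Four stronger readings are tempting, and the documents do not support them.

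- **That a single cross-group swap brings the bad data back by itself.** It is 5% per group, below the trigger.
- **That the RSV/placebo GMT ratio would be visibly distorted.** For R = 10 the apparent ratio would be 10 × 10^(−0.1) = 7.9, but SAP 5.3.1.1 lists no between-group ratio. It plans within-group GMTs and GMCs and post/pre ratios, with placebo as a reference in scatter plots.
- **That every 2120 result is known to be wrong.** This fits a confirmed mismatch. For mishandling the SAP says only that the data are unreliable.
- **That a bad Visit 1 value also contaminates the PPS fold increases, because 2120 removes that visit alone.** Removing Visit 1 removes the baseline, and missing results are not replaced, so the natural reading is that those fold increases are not computed. The SAP leaves this unstated, which is a gap in wording and not a demonstrated error.

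**Conclusion.** The point holds in a limited form. Under SAP 4.2.1 and 4.2.2.1, an ES immunogenicity analysis run as written includes results already confirmed as mismatched or mishandled, and an affected Visit 1 value carries into that subject's three later fold increases in the ES. No other SAP rule prevents this.

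Under the stated assumptions, one cross-group swap moves each group's GMT by about 8% to 16% (11% to 12% at a true ratio of 10) and widens its log-scale interval by about 10% to 30%. The titre SD, the ratio R and the baseline error factor F are all assumed; the effect of mishandling at the laboratory is not quantified. Severity is minor.

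**What to change.** Add one sentence to SAP 5.3 or 10.1.2.2: any serology result under code 2120 is set to missing in every immunogenicity analysis, on the ES as well as the PPS, and fold increases that use an affected Visit 1 result are not computed. This also settles the unstated PPS handling.

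Do not relabel 2120 in the code table as an ES elimination code. Codes with that label remove the whole subject from the ES under SAP 4.2.1, and the ES also serves the safety analysis (SAP 5.4) and the RTI analysis (SAP 5.5). The subject should stay in the ES for safety, RTI and all unaffected serology.

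The cost is one sentence. The ES immunogenicity analysis loses only results already confirmed as unreliable and the fold increases that depend on them. Sample size and safety outputs do not change.
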